10.4 Timing of Study Procedures

The target date for completion of the pre-baseline testing (i.e., screening) assessments will be anchored to the date of admission to the hospital for hip fracture. The target date for completion of all other assessments will be anchored to the date on which all baseline testing is completed (see Table 1).

Note: In cases where the participant performs all required baseline measures and then performs additional baseline measures, the date on which baseline testing is completed is defined as the date on which the participant performed the last assessment within the allowable window for baseline testing (up to 26 week post hospital admission). In cases where additional baseline measures have been scheduled but cannot be completed within the allowable window for baseline testing, (e.g., scheduling conflict, not safe), the date on which baseline testing completed is defined as the date on which staff establishes definitively that no additional baseline measures can or will be attempted.

Table 1. Timing of Study Procedures

PROCEDURE	TARGET DATE	ALLOWABLE INTERVAL
Phase 3 screening	As early as possible following admission	Up to 26 weeks post-admission
Baseline assessment	As early as possible following admission	Up to 26 weeks post-admission
Dietitian consult	1 week after baseline testing is completed	+1 week
First intervention visit	1 week after baseline testing is completed	+16 weeks
First telephone interview	4 weeks after baseline testing is completed	-1 week, +3 weeks
Subsequent telephone interviews	At 4-week intervals from date on which baseline testing is completed	-1 week, +3 weeks
First follow-up assessment	16 weeks after baseline testing is completed	+2 weeks
Out-of-window assessment	16 weeks after baseline testing is completed	0-16 weeks and 18-38 weeks after baseline testing is completed

At baseline, all participants will, by design, be tested at the clinical site. At the follow-up visit, we will attempt to test all participants at the clinical site. When this is not possible, we will attempt to have study staff administer the test in a non-study clinical facility or, failing that, at another non-study location or the participant's home.

Section 11: Safety Assessments

11.1 Participant Safety Parameters: Methods and Timing

11.1.1 Pre-Intervention Safety Screening

Potential participants will be excluded during the screening phases if they have cardiovascular diseases or other conditions that would make it unsafe for them to participate in one or both of the study interventions. Information about these conditions will be obtained through chart review, interviews, and consultation with a medical professional familiar with the potential participant (e.g., primary care provider, orthopaedic surgeon). The study physician and PI will be responsible for giving permission for potential participants to receive the intervention, based on thorough review of all eligibility information. In addition, persons who develop chest pain or substantial shortness of breath during the SMWT will be excluded using a protocol to evaluate cardiovascular reserve similar to the one suggested by Gill et al.¹⁶²

11.1.2 Safety Considerations for Study Assessments

All study assessments will be done by certified staff who will be trained to perform the tests safely. If, during the SMWT or the SPPB a participant reports chest pain, tightness or pressure, significant shortness of breath or difficulty breathing, or feeling faint, lightheaded, or dizzy, the test will be stopped. If the participant weighs more than 400 pounds or if s/he is unable to lie supine, the whole body and hip DXA scans will not be done. Participants with prior hardware in the non-fractured hip will not have a hip DXA scan. If a participant is unable to lie supine or be left alone in a room, the thigh CT scan will not be done. Participants unable to put full weight on the fractured side or unable to stand for 30 seconds without an assistive device will not perform the GAITrite or Biodex measures. All research staff who come in contact with study participants will be CPR certified and will be trained to provide immediate care when faced with medical emergencies. Also, institutional and community emergency medical services will be activated if needed.

Table 2 describes a summary of safety alerts and the appropriate action during clinical assessments.

Table 2. Safety Alerts and Actions for Study Assessments

ALERT	ACTION
Resting blood pressure SBP > 145mm Hg or DBP > 90mm Hg	Qualified staff will inform the participant if noted on more than one occasion.
Resting blood pressure SBP > 170mm Hg or SBP < 90mm Hg or DBP > 100mm Hg or DBP < 50mm Hg	Qualified staff will encourage the participant to seek additional follow-up and/or medical evaluation. Physical performance testing will be deferred until consultation with the study physician.
Resting blood pressure or after SMWT SBP > 185mm Hg or SBP < 90mm Hg or DBP > 110mm Hg or DBP < 50mm Hg	Qualified staff will consult with the study physician and follow up as needed.
Resting pulse Rate > 120 or < 40 beats/min	Qualified staff will consult with the study physician and follow up as needed.

Table 2. Safety Alerts and Actions for Study Assessments

Chest pain, dizziness, significant shortness of breath, or severe musculoskeletal pain during the intervention or study assessment.	Qualified staff will consult with the study physician and follow up as needed.
MNA®-SF Score \leq 7 at the follow-up assessment	Qualified staff will talk to the participant and provide a referral for additional follow-up and/or medical evaluation for possible malnutrition.
Weight loss \geq 2% body weight in four weeks during intervention period	Participant will be referred to the registered dietician for follow-up by telephone.
Participant expresses desire to commit suicide	Call primary care provider and report findings. Report to study coordinator/study physician for follow-up and clearance.

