11.1.4 Safety Measures during the PUSH Intervention

The PUSH intervention will be conducted in the participant's place of residence and all sessions will be conducted and supervised by trained PTs, who monitor potential adverse experiences and symptoms. PTs will be trained to deal with medical emergencies that occur during the PUSH sessions and will be CPR certified. Also, community EMS services will be activated if needed.

In order to minimize discomfort and maximize safety, participants will be taught the proper method for performing each exercise and the importance of following the proper method. Intensity is gradually increased, and exercise technique is commented on during each session. Participants will be instructed to talk with the PTs about any muscle soreness, pain or discomfort.

Every effort will be made to prevent harm by stopping intervention activity when the participant reports chest pain, dizziness, significant shortness of breath, or severe musculoskeletal pain. PTs will monitor blood pressure at the start of the training session, mid-session, and when participants are finished with the session. Blood pressure and heart rate will be monitored using a standard blood pressure cuff and palpation of peripheral pulse. If blood pressure is elevated above 170/100, the participant will rest quietly for a few minutes. The PT will monitor the participant for signs of muscle strain, dizziness, or hypotension and appropriate palliative methods will be discussed with the participants and appropriate medical referrals will be made. Please see Table 3 for a summary of alerts and appropriate action during the PT intervention visits.

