11.1.5 Safety Considerations for the Protein Intervention

Although the protein supplement used in this study is virtually lactose (sugar) free, small amounts of lactose may trigger digestive upset (abdominal pain, gas, and diarrhea) for participants who suffer from lactose intolerance. Although this product may not contain one or all of the following, this product is manufactured in a facility that handles milk, soy, egg, peanut, nut, tree, fish, crustaceans/shellfish, and wheat products. Those who have celiac disease or who have a known allergy to dairy, peanuts, or shellfish are excluded from participation. Whey provides no fiber to the diet, and excessive consumption may lead participants to experience constipation unless they consume high-fiber foods in addition to whey. There is an extremely low risk of renal (kidney) or liver damage related to whey protein supplementation. Those with a history of severe liver disease (e.g., hepatitis, fatty liver disease, cirrhosis), chronic kidney disease (CKD stage 4), or a calculated creatinine clearance 15-29 ml/min are excluded from participation. There is an extremely low risk that participants with poorly controlled type 2 diabetes could experience hypoglycemia (low blood sugar). Those with hemoglobin A1c level greater than 10% are excluded from participation. Please see Table 3 for a summary of alerts and appropriate action for the protein intervention.

Table 3. Safety Alerts and Actions for Interventions

ALERT	ACTION
Resting blood pressure SBP > 170mm Hg or SBP < 90mm Hg or DBP > 100mm Hg or DBP < 50mm Hg	
 1. If initial BP check is high (systolic > 170; diastolic >100), have participant sit for 5 minutes and rest then check BP again. This may be done twice. 2. If three BP readings are greater than 170/100, then individual should not exercise. 3. The PCP, study coordinator, and study physician should be called before exercise is initiated. 4. If initial BP is low for that person (systolic<90; diastolic<50) follow same protocol.
New chest pain	Call 911.
Reported chest pain that occurred between visits	
 1. Cancel treatment and call PCP. 2. Report to study coordinator and study physician to follow-up until cleared.

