Acute shortness of breath	
 1. Have participant stop exercising and rest. 2. Take vital signs. 3. If the shortness of breath does not resolve itself in 10 minutes, and vital signs are not within normal limits for participant, call 911. 4. Report to PCP, study coordinator, and study physician.
Fall	
 1. If there is bleeding/wound, apply pressure using emergency kit for wound; call 911 if needed. If participant is unable to stand or move the injured part, call 911 and keep them warm and comfortable. 2. Report all falls to study coordinator. 3. Complete an incident report.
Stroke symptoms	Call 911 immediately.
Dizziness during exercise	
 1. Stop exercise and have person sit or lie down. 2. If sitting is not sufficient to resolve dizziness, then check vital signs. 3. Call 911 if clinically unstable. 4. Report to PCP if heart rate is less than 60 (and not usually so), the dizziness is new in onset; or if the BP is > 160/100 or systolic <90. 5. Report event to study coordinator and study physician.

ALERT	ACTION
Resting pulse Rate > 120 or < 40 beats/min	
 1. PT will stop delivery of the intervention. 2. Qualified staff will consult with the study physician and follow up as needed. 3. PT will resume delivery of the intervention only after the participant receives medical clearance.
New irregular heart rate with complaint of heart palpitations	
 1. Do not exercise and call PCP. 2. Report to study coordinator and study physician for follow-up. 3. Wait for medical clearance to resume exercise.
New acute musculoskeletal pain during exercise (pain > 5 on VAS)	
 1. Have the participant stop the exercise and rest. 2. Attempt to alter position of participant to reduce pain. If pain persists, do not continue specific exercise. Attempt to do other exercises. 3. If pain does not resolve, refer to PCP or orthopedist and study physician.
New, acute, non-musculoskeletal pain (pain > 5 on VAS)	
 1. Do not exercise. 2. Take pain history and call PCP. 3. Report to study coordinator and study physician for follow-up and clearance.
Acute change in mental status	
 1. Do not exercise. 2. Call PCP or if unavailable, call 911. 3. Report to study coordinator and study physician for follow-up and clearance.

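### Table 2's symptom row reaches into intervention visits and conflicts with Table 3 on chest pain: consult the study physician in one, call 911 in the other

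*Protocol*

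**What the plan says.** **Scope of Table 2.** Section 11.1.2 introduces it thus: "Table 2 describes a summary of safety alerts and the appropriate action during clinical assessments". The table's title also limits it to study assessments. One row nevertheless applies to "Chest pain, dizziness, significant shortness of breath, or severe musculoskeletal pain during the intervention or study assessment". Its action, in full, is "Qualified staff will consult with the study physician and follow up as needed". The text above the table adds a general provision: "Also, institutional and community emergency medical services will be activated if needed".

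**Scope of Table 3.** The table sits in Section 11.1.5 and its title names the interventions. Section 11.1.4 says: "Please see Table 3 for a summary of alerts and appropriate action during the PT intervention visits". Section 11.1.3 closes with the same direction.

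**Actions in Table 3.** For "New chest pain" the action is to call 911. The row has no condition and no study-physician step. Acute shortness of breath has four steps, the third being "If the shortness of breath does not resolve itself in 10 minutes, and vital signs are not within normal limits for participant, call 911" and the last a report to the primary care provider (PCP), the coordinator and the study physician. Dizziness during exercise has five steps: 911 is called if the participant is clinically unstable, and the event is reported to the coordinator and the study physician.

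**Text for intervention sessions.** Section 11.1.4 separately requires "stopping intervention activity when the participant reports chest pain, dizziness, significant shortness of breath, or severe musculoskeletal pain" and repeats that emergency services are activated when needed.

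**The concern.** The Table 2 row names the intervention as well as the assessment, so it overlaps Table 3. Where the two tables give different actions for the same event, staff have two written instructions and no sentence that ranks them. For chest pain the instructions differ in urgency: one is a consultation with follow-up at discretion, the other an unconditional emergency call.

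Sessions take place in the participant's residence under a study PT, and chest pain or discomfort is on the list of expected adverse events in Section 12.3, so the situation is foreseeable. An emergency instruction should have one reading. Safety and tolerability are also a stated objective (Section 4.2), so the protocol's own safety instructions ought to agree with each other.

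**Working it through.** No figure in the plan bears on this point and no formula applies. The check sets the two tables side by side for an event during an intervention visit.

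| Symptom | Table 2 row | Table 3 row | Comparison |
|---|---|---|---|
| Chest pain | Consult study physician, follow up as needed | Call 911, no condition, no physician step | Direct conflict |
| Acute or significant shortness of breath | Same | Stop, rest, vital signs; 911 if two conditions are both met; report to PCP, coordinator, study physician | Different steps and sequence; physician contact in both |
| Dizziness | Same | Stop, sit or lie down; vital signs if sitting is not enough; 911 if clinically unstable; PCP under stated conditions; report to coordinator and study physician | Different steps and sequence; physician contact in both |
| Musculoskeletal pain | Same | Stop, rest, change position, try other exercises; referral, including to the study physician, if unresolved | Stepwise; no 911 step |

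The remaining checks ask whether anything else in the protocol settles the chest-pain row.

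1. *Is it the same event?* Table 3 has a separate row for chest pain that occurred between visits, with its own action (cancel treatment, call the PCP, report). The new chest pain row is therefore the one that meets chest pain arising at a visit. Table 2's row covers chest pain during the intervention. The two overlap.
2. *Does Table 2's title confine it to assessments?* The title and introduction say so, but the row's own words do not. Another Table 2 row, on weight loss over four weeks, also refers to the intervention period. The table does reach beyond assessment visits.
3. *Is the Table 2 action usable at a home visit?* Yes. Section 12.7.1 makes the study physician available by telephone whenever participants are engaged in the home-based interventions. The row cannot be set aside as inoperable there.
4. *Do the general emergency-service sentences settle it?* They are tied to no symptom and leave the decision to judgment. Table 3's chest-pain row leaves no such judgment.
5. *Does another section rank the tables?* Section 13 sends stopping criteria to the MOP, which is not among the documents. No sentence says that Table 3 overrides the Table 2 row.

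**The case against.** The strongest reply is that the protocol does tell the PT where to look. Sections 11.1.3 and 11.1.4 both point PT visits to Table 3, Table 3's title names the interventions, and nothing points a PT to Table 2. On that view the words extending the Table 2 row to the intervention are a drafting slip. This carries weight: it makes Table 3 the likelier guide in practice and weakens any claim that therapists would choose freely between the tables. It does not remove the row's express wording.

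A second reply is that the two actions can be combined. Consulting the physician does not forbid a 911 call, activity must stop in any case under Section 11.1.4, and Table 3's pulse row pairs a PT action with a consultation by qualified staff. The Table 2 row could then be read as an added notification. That reading is possible, but the row lists no other step and does not present itself as an addition.

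Third, PTs are trained and certified, and the MOP may already be clear. That cannot be judged from these documents, and it would not make the protocol consistent with itself.

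A reader might infer more than the documents support, in three ways:

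- *That all the shared symptoms set the physician against 911.* Table 3 makes 911 conditional for shortness of breath and dizziness and sends both to the study physician.
- *That the size is 30 participants × 32 visits = 960 sessions.* That counts planned sessions, not events. No symptom rate is given. Section 11.1.3 cites one cardiac event per 60,000 participant-hours in aerobic programmes; at about one hour per visit this would give 960 / 60,000 = 0.016 events. It describes cardiac events, not chest pain or dizziness as symptoms, so it does not measure exposure either.
- *That the record of stopped or suspended interventions would vary by therapist.* Section 12.6.1 gives removal from the intervention to the PI, in consultation with the study physician and the independent safety monitor, and Section 12.4 defines reportable events without reference to either table.

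**Conclusion.** The inconsistency is real and limited. For one symptom, chest pain during an intervention visit, Table 2 and Table 3 give different actions of different urgency, and neither the cross-references nor the general emergency-service sentences remove the conflict. For acute shortness of breath and dizziness the tables differ in steps and sequence but are partly compatible.

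The point should be classed as an internal inconsistency affecting participant safety, not as a design choice or a statistical flaw. It has no bearing on the primary comparison, the sample size or the analysis. How often it would matter is unknown. The conclusion rests on reading the Table 2 row as written, and on the absence, in the protocol, of a rule that ranks the tables. It takes no position on which clinical action is right.

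**What to change.** Reconcile the scope and action of the Table 2 symptom row with Table 3, so that each event during an intervention visit has one written action. The drafting can be done through the scope of the row, through the actions, or both. The sponsor's clinicians should decide the content; this review does not choose between the tables. The same edit should settle how the row relates to the stepwise Table 3 rows for shortness of breath and dizziness, and to the stop instruction in Section 11.1.4. Carry the reconciled text into PT training and the MOP, and check that the MOP stopping instructions cited in Section 13 agree with it.

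The cost is a wording change to one table row, approval of the modification by the institutional review boards under Section 16.1, and a short refresher for active PTs. No new data, procedures or participants are needed.

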11.1.3 Safety Considerations for the PUSH Intervention

There is no expectation that the PUSH intervention will evoke serious cardiovascular responses; however, participants will be warned of a possible risk. Cardiac events are rare, with estimates of one event per 60,000 participant-hours in aerobic exercise programs.¹⁶³ No significant cardiac events were reported after performing 1-RM testing for over 6600 healthy subjects.¹⁶⁴ The American Heart Association's guidelines for resistance training for adults with and without cardiovascular disease reports the safety of high intensity resistance training and testing in persons with coronary disease which found an absence of anginal symptoms, ischemic ST-segment depression, abnormal hemodynamics, complex ventricular dysrhythmias, and cardiovascular complications.^{165,166} Less serious risks may include chest pain, fainting, hypotension, or muscle strain. We have minimized risk to participants by following the guidelines suggested by Gill et al.¹⁶² Blood pressure and heart rate will be monitored using a standard blood pressure cuff and palpation of peripheral pulse.

Another concern is the presence of osteoporosis and the risk of inducing a compression fracture or a lower extremity fracture. The exercises have been designed to minimize this risk. The risk of inducing a compression fracture will be minimized because the exercises are performed in supine and upright standing positions with minimal to no trunk flexion.¹⁶⁷ The PT will also remind the participant to minimize flexion to the spine during all standing exercises. Using an exercise device that eliminates the risk of weights falling on a person, and using only voluntary muscle contractions during isometric testing, will reduce the risk of lower extremity fracture. We do not anticipate additional risk for the PUSH intervention for the following reasons: 1) by 12 weeks post-fracture, there is moderate stability from the bone callus formation, 2) participants will only be included if they have medical clearance to participate in full weight bearing activities, and 3) the device limit is 100 pounds (which in most cases is less than body weight) resulting in less load than walking up and down stairs. Delayed onset muscle soreness is a common occurrence after the initiation of an exercise program. The soreness occurs in the muscle belly 1-3 days after the initiation of exercise and lasts 2-3 days. There is no effective way to eliminate the risk of delayed onset muscle soreness, but it is hoped that the orientation process and gradual increase in intensity will reduce the risk. The participants will be informed about the condition, what it feels like, how long it lasts, and suggested ways of decreasing the pain including the use of superficial heat or ice. If a participant reports continued discomfort, the study physician will discuss this with the participant and contact their primary care provider (PCP) as necessary. Please see Table 3 below for a summary of alerts and appropriate action during the PT intervention visits.

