Muscle performance will focus on bilateral hip extensors, hip abductors, knee extensors, and plantar flexors because of their role in function, specifically gait and transfer activities.¹²²⁻¹²⁴ Hip and knee extensor muscle will be trained to work hard and fast during the leg press motion since this mimics the functional activity of rising from a chair or going up a step. Hip abductors will be trained in 5° of adduction and to 10-15° of abduction. Fifteen degrees of movement was chosen because it approximates the 8° of motion associated with gait and takes into account variations in hip positions while standing.¹²⁵ Hip extension will also be trained in standing from 35° of flexion to extension to a neutral position. This ROM approximates the time in the gait cycle when the gluteus maximus shows the highest muscle activity, i.e., from heel contact through 20% of stride.¹²³ Plantar flexors will be strengthened in standing against body weight⁶⁸ because of their role in the push-off phase of gait and the strong association of plantar flexion power and walking speed.^{68,122-126} The intensity of strength training will be determined during Day 1 of intervention at the participant's residence. The PT will determine the amount of resistance the participant can push against so that s/he can complete a maximum of eight repetitions (eight repetitions maximum (RM) or 8-RM). 8-RM was chosen because it is strongly related to the 1-RM¹²⁷ and determining the 8-RM will allow the PT to know the training intensity without further sub-calculations (e.g. 80% of the 1-RM). Studies have shown that the 8-RM is more effective than training at 10-RM or 2-RM⁷⁹ yet is not so aggressive that it is associated with injuries.^{128,129} This protocol has been used safely and effectively in elders^{12,64,65,68,124,130} and specifically in persons post-hip fracture.^{20,63} For the first visit, participants will be tested to find the load associated with an intensity of 8-RM. During the second session, participants will

Figure 3. Shuttle Device (arrows indicate direction of lower extremity motion)

perform 2 sets of 8 repetitions at the 8-RM intensity. From the third session through the remainder of the program,

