9.6.4 Expected Adverse Events (AEs)

Expected AEs will be assessed every four weeks during the telephone interview. Participants (or their proxies) will be asked a series of standardized questions related to pain (feet, hip, back, knees, digestive and stomach); breathing problems or chest pain; bloating or puffiness in legs, ankles, or feet; drowsiness, dizziness, or confusion; shakiness, anxiety, clammy skin, or irritability; and falls (with and without injury).

Section 10: Study Procedures

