12.2.2 Expectedness

An independent safety monitor (ISM) will assess AEs as to whether they were expected or unexpected based on current knowledge. Categories are:

Expected: An AE that is anticipated on the basis of prior experience with the intervention under investigation; an event that can be attributed to the underlying condition of the participant being

studied; or an event that can be attributed to the patient population being studied (see section 12.3). Expected AEs are captured in a standardized way every four weeks.

Unexpected: An AE that was not anticipated on the basis of prior experience with the intervention under investigation; an event that cannot be attributed to the underlying condition of the participant being studied or to the patient population; or an expected event whose frequency or severity exceeds what was anticipated (see section 12.4.2). Unexpected AEs are reportable.

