12.3 Expected AEs

Expected AEs will be captured through telephone interviews every four using the Expected Adverse Events Form. Following are expected adverse events that have been listed in the ICF:

- foot pain
- hip pain
- back pain
- knee pain
- digestive or stomach pain
- breathing problems
- chest pain or discomfort
- bloating or puffiness in the legs, ankles, or feet
- drowsiness, dizziness, or confusion
- shakiness, anxiety, clammy skin, or irritability
- fall (with or without injury)

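### The standard adverse-event questions omit bowel symptoms and muscle soreness that the protocol itself anticipates, so these would be under-counted for the safety and tolerability objective

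*Protocol*

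**What the plan says.** Protocol 4.2 makes the safety and tolerability of PUSH Plus Protein one of the study's objectives.

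**Effects the protocol anticipates.** For the exercise, 11.1.3 states: "Less serious risks may include chest pain, fainting, hypotension, or muscle strain". It then calls delayed-onset soreness common when an exercise program starts: "The soreness occurs in the muscle belly 1-3 days after the initiation of exercise and lasts 2-3 days". For the supplement, 11.1.5 says that in people with lactose intolerance "small amounts of lactose may trigger digestive upset (abdominal pain, gas, and diarrhea"), and that "excessive consumption may lead participants to experience constipation unless they consume high-fiber foods in addition to whey". Section 11.1.7 separately names mild constipation or diarrhea for the vitamin D, calcium and multivitamin.

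**What participants are asked.** The telephone questions in 9.6.4 cover "pain (feet, hip, back, knees, digestive and stomach); breathing problems or chest pain", then swelling of the lower legs and feet, dizziness and related symptoms, shakiness and related symptoms, and falls. Section 12.3 repeats this as 11 items, introduced by "Following are expected adverse events that have been listed in the ICF".

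**How events are classed.** Under 12.2.2 an expected event includes "An AE that is anticipated on the basis of prior experience with the intervention under investigation", and that section says expected events are collected in a standard way every four weeks. Section 12.8 gives the DSMB a semiannual table of non-serious and expected events. Section 14 and the SAP describe no safety or tolerability summary.

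**The concern.** By the protocol's own definition, a symptom it anticipates from the intervention is an expected event and should be collected routinely. Several such symptoms are not on the form that does the collecting. If the form is used as described, they are counted only when a participant volunteers them, a therapist notes them, or they happen to be felt as pain at a listed site.

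The supplement is the one component this pilot adds to PUSH, and bowel symptoms are the ordinary reason for finding a whey powder hard to take. Lactose intolerance is not an exclusion in 7.3 (dairy allergy is), so the group for whom 11.1.5 predicts gas and diarrhea can enroll. An under-count would make the supplement look better tolerated than it is, both in the DSMB table and in the information used to plan the definitive study.

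**Working it through.** The plan states no figure on this point, so the check sets the text side by side.

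**Step 1. Each anticipated effect against the standard questions (9.6.4, 12.3) and the other routes.**

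| Effect | Named in | Nearest standard question | Other route | Result |
|---|---|---|---|---|
| Gas | 11.1.5 | Digestive or stomach pain | Participant report (11.3); protein AE monitoring (11.1.6) | Not asked |
| Diarrhea | 11.1.5, 11.1.7 | Digestive or stomach pain | As above | Not asked |
| Constipation | 11.1.5, 11.1.7 | Digestive or stomach pain | As above | Not asked |
| Muscle soreness | 11.1.3 | Foot, hip, back or knee pain | Told to the therapist (11.1.4); 11.3 | Not asked; some cases caught as site pain |
| Muscle strain | 11.1.3 | Foot, hip, back or knee pain | Therapist watch (11.1.4); reportable if a supervised injury (12.4.3) | Partly covered |
| Fainting | 11.1.3 | Dizziness; falls | 11.3 | Partly covered |
| Hypotension | 11.1.3 | Dizziness | Blood pressure three times per session (11.1.4); Table 3 action | Measured and acted on |
| Chest pain | 11.1.3 | Chest pain | - | Asked |
| Abdominal pain | 11.1.5 | Digestive or stomach pain | - | Asked |

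The only item that mentions bloating concerns the legs, ankles and feet, so it does not stand in for gas.

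**Step 2. Would site pain pick up soreness?** Section 8.3 says: "Muscle performance will focus on bilateral hip extensors, hip abductors, knee extensors, and plantar flexors because of their role in function". Soreness in the hip muscles might be reported as hip pain. The knee extensors and plantar flexors lie in the thigh and calf, and 11.1.3 places the soreness in the muscle belly. No question asks about the thigh or calf.

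**Step 3. Would the unexpected-event route pick up the rest?** Section 12.4.2 defines unexpected events as ones that are uncommon in this population and absent from the consent form and 12.3. Soreness that the protocol calls common fails the first condition. Gas or diarrhea could be argued either way, since 11.1.5 anticipates them but 12.3 omits them. To become reportable, an unexpected event must also point to greater risk than was already known. A mild effect that the protocol already names would seldom do so.

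**Step 4. What reaches the count.** There are four calls per participant (every four weeks for 16 weeks), so 30 x 4 = 120 calls. As described, none asks about gas, diarrhea, constipation or muscle soreness. This affects how a low count can be read. If all 30 were asked and none reported a symptom, the exact two-sided 95% upper limit would be 1 - 0.025^(1/30) = 11.6%. If they were not asked, a zero supports no such limit.

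**The case against.** The case against is substantial, and much of it stands.

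- **Other routes exist and are not limited to the 11 items.** Section 11.3 instructs every participant to report any AE at scheduled contacts, to the therapist, or at any time. Therapists visit twice a week, and participants are told to discuss soreness with them. Section 11.1.6 adds AE monitoring for the protein. This rules out any claim that these effects go unmonitored. It does not supply a uniform question or a denominator.
- **Some named effects are not real gaps.** Hypotension is a measured sign rather than a telephone symptom. Strain in a supervised session is reportable as an injury. Fainting overlaps with dizziness and falls. Constipation is tied to excessive intake, and the study gives one 27.6 g dose a day; however, 11.1.7 names it again for the tablets.
- **Tolerability is partly measured already.** Section 9.6.1 weighs the protein containers every four weeks and takes self-reported adherence. That shows whether people stopped or cut back, but not whether symptoms were the cause.
- **The form, consent document, Manual of Procedures and Figures 5a-d could not be seen.** The form may hold more than 9.6.4 and 12.3 describe, and the DSMB approves the list (12.1).

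A reader might infer four stronger things that the documents do not support. First, that participants are unsafe: the clinical monitoring above argues otherwise. Second, that soreness is lost through weeks of recall before a telephone call: twice-weekly visits give a much earlier contact. Third, that Table 3 alerts missing from the AE list are lost harms: they are triggers for action, and those without a counterpart on the list go to the study physician. Fourth, that the missing safety section in Section 14 and the SAP is itself a serious flaw: with DSMB tables planned and 30 participants, it is mostly missing detail.

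**Conclusion.** The concern holds in a limited form. Gas, diarrhea, constipation and muscle soreness are anticipated in the protocol but absent from the standard questions, contrary to the rule in 12.2.2. Strain and fainting are partly covered. These mild effects would be under-counted in the DSMB table and for the 4.2 objective.

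The number of missed events cannot be given, because the documents state neither event rates nor the share likely to be volunteered. The conclusion assumes that the telephone form follows 9.6.4 and 12.3. If the actual form already asks about these symptoms, only the text needs correcting. The issue is completeness of counting, not safety of care, and it is worth correcting because the bowel symptoms concern the component under test.

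**What to change.** With DSMB approval, as 12.1 requires:

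1. Add to the Expected AE form, 9.6.4 and 12.3: (a) diarrhea, constipation or gas; (b) muscle soreness or strain. Name fainting explicitly alongside dizziness. Otherwise leave the existing 11 items as they are.
2. Have therapists note soreness, low blood pressure, and held or modified sessions in the visit logs that 9.6.1 already requires. That section does not name blood pressure as a recorded field, so add it if the log lacks it.
3. Report these, together with protein adherence from 9.6.1, in one descriptive safety and tolerability table in Section 14 and the SAP. No model or test is needed. With 30 participants the intervals will be wide: 6 of 30, for example, has an exact 95% interval of 7.7% to 38.6%.

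The costs are slightly longer calls, more minor events counted and possibly a consent update. Two limits remain. Bowel events could not be attributed to the protein alone, because participants also take vitamins and, unless contraindicated, calcium. The documents also do not say whether CAP asked these questions, so there may be no comparator. No alert threshold or clinical action changes.
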